7.9.7 Precision Analysis

Precision analysis will be performed for the two sensors worn by the same subject in the same location.

7.9.8 Comparison of CGM Performance to Reference under conditions leading to Alert

The alert will be triggered when the sensor BG value reaches the threshold glucose value. Predictive alerts will be evaluated by using the predicted sensor BG value based on current sensor BG and sensor BG readings within the previous 30 minutes.

In the in-clinic portion, the threshold and predictive alert analysis will be performed retrospectively with theoretical hypoglycemia threshold setting at 50 mg/dL, 60 mg/dL, 70 mg/dL, 80 mg/dL, 90 mg/dL and 100 mg/dL and theoretical hyperglycemia threshold setting at 180 mg/dL, 220 mg/dL, 250 mg/dL and 300 mg/dL.

The threshold alert performance will be evaluated for in-clinic portion by true alert rate, missed alert rate and false alert rate within 15 and 30 minute windows of the reference event. Predictive alert performance will only be evaluated for the in-clinic portion by true predictive alert rate, missed predictive alert rate and false predictive alert rate within 15 and 30 minute windows. All reference BG values will be used, including those less than (<) 40 mg/dL and greater than (>) 400 mg/dL.

The comparison of CGM performance to reference under conditions leading to alert will be evaluated by true alert rate, missed alert rate and false alert rate within 15 and 30 minutes window of the reference event.

The alert rates will be defined as follows:

Alert Rate Type	Column Label	Label Definition
Detection Rate	Hypo/Hyper Events Correctly Detected (%)	The device alarmed at the specified CGM settings within 30 minutes (or 15 minutes) before or after the reference blood glucose value (YSI™* or SMBG) goes below (for hypo) or above (for hyper) the specified CGM setting levels.

Alert Rate Type	Column Label	Label Definition
Missed Detection Rate	Hypo/Hyper Events Not Detected (%)	The device did not alarm at the specified CGM settings within 30 minutes (or 15 minutes) before or after the reference blood glucose value (YSI™* or SMBG) goes below (for hypo) or above (for hyper) the specified CGM setting levels.
True Alert	Alerts Verified by Hypo/Hyper Events (%)	There is at least one reference blood glucose value (YSI™* or SMBG) goes below (for hypo) or above (for hyper) the specified CGM setting levels within 30 minutes (or 15 minutes) before or after the sensor alarmed at the specified alert settings.
False Alert	False Alerts (%)	There is no reference blood glucose value (YSI™* or SMBG) goes below (for hypo) or above (for hyper) the specified CGM setting levels within 30 minutes (or 15 minutes) before or after the sensor alarmed at the specified alert settings.

7.9.9 Other Accuracy Analyses

The ARE, the absolute differences between the sensor and YSI™* relative to the YSI™* reference will be calculated for each day separately. Summary statistics will include its mean, standard deviation, min, median, and max.

The mean numerical bias, which is the difference between the sensor and YSI™* values, will be calculated for each day. Summary statistics will include its mean, standard deviation, min, median, and max.

A correlation between the sensor and YSI™* values will be performed. As this statistic ignores any data dependency, it will be used only as a descriptive measure of association.

A linear model, in which YSI™* is predicted by sensor values, using a repeated measures model, will be performed. The models solution will provide the intercept and slope, while adjusting for dependence in the data within day. An intercept of 0, along with a slope of 1, would indicate the absence of bias in predicting YSI™* from sensor readings. The residuals of the model will be inspected to determine if transformation of either variable is required.

Bland-Altman plots, with 95% CI, will be provided for each of the 3 study days. The paired differences between the sensor and YSI™* rating will be plotted against the X-axis reference of mean YSI™* and sensor values.

Descriptive subgroup analysis of Guardian™ Sensor (3) performance (20% mean agreement rate (± 20 mg/dL when Reference BG less than ($<$) 70 mg/dL)) will be performed in the following cohorts:

- **Diabetes cohorts based on insulin requirement**
 - 18-80 years
 - Insulin requiring N = minimum 78 subjects
 - N= minimum of 52 type 1 insulin requiring
 - N= minimum of 26 type 2 insulin requiring
 - Non-Insulin requiring N = minimum 12 subjects
 - 14 - 17 years
 - Insulin requiring N = minimum 24 subjects
 - 2 - 13 years
 - Insulin requiring N = minimum 10 subjects
- **Diabetes cohorts based on Centers for Disease Control and Prevention (CDC) classification for 20 years old or younger**

A description of the following 4 groups will be performed:

 - Underweight subjects (less than ($<$) 5th percentile): N=minimum of 1 subject
 - Normal weight subjects (5th percentile to less than ($<$) 85th percentile): N= minimum of 40 subjects
 - Overweight (85th to less than ($<$) the 95th percentile): N= minimum of 8
 - Obese subjects (greater than or equal to (\geq) the 95th percentile): N=minimum of 1 subject
- **Diabetes cohorts based on BMI according to WHO criteria [World Health Organization, 2011] for subjects greater than 20 years old:**

A description of the following 5 groups will be performed:

 - Underweight subjects (BMI less than ($<$)18.5 kg/m²): N=minimum of 1 subject
 - Normal weight subjects (BMI 18.5 to 24.99 kg/m²): N= minimum of 28 subjects
 - Overweight and obese subjects (BMI 25.00 to 40 kg/m²): N= minimum of 36 subjects

- Overweight subjects (BMI 25.00 to 29.99 kg/m²)
- Obese subjects (BMI 30.00 to 39.99 kg/m²)
- Morbidly obese subjects (BMI greater than or equal to (\geq)40 kg/m²): N=minimum of 1 subject

- **Diabetes cohorts based on prior real-time CGM experience (by self report)**
 - CGM naïve: N= minimum of 40 subjects (2-80 years)
 - CGM experienced: N= minimum of 40 subjects (2-80 years)

- **Diabetes cohorts based on HbA1c:**
 - Baseline HbA1c (by certified National Glycohemoglobin Standardization Program, NGSP, method) will be collected:
 - A description of the following 3 groups will be performed: HbA1c less than (<) 7%, HbA1c 7-9%, HbA1c greater than (>) 9%
 - Quartile comparison (lowest to the highest) based on HbA1c

- **Diabetes cohort based on exercise activity:**
 - 18 – 80 years
 - N=minimum of 22 subjects
 - 14 - 17 years
 - N= minimum of 6 subjects
 - 2 - 13 years
 - N= minimum of 20 subjects
 - Sponsor may instruct site for exercise to be performed in order to obtain low glucose values

- **Diabetes cohort based on compression procedure:**
 - 18 – 80 years
 - N=minimum of 22 subjects
 - 14 - 17 years
 - N= minimum of 6 subjects
 - 2 - 13 years
 - N= minimum of 10 subjects

All analyses follow the definitions provided in: Performance Metrics for Continuous Interstitial Glucose Monitoring: Approved Guideline, CLSI POCT05-A [Klonoff et al. 2008].

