**Subjects will be assigned to the following according to their age:****Subjects 14 - 80 years**

- Sensor Location (14-17 years) - **Random Assignment**
  - Arm/Arm/Buttock
    - N=4 minimum
  - Buttock/Buttock/Arm
    - N=4 minimum
- Sensor Location (18-80 years) - **Random Assignment**
  - Arm/Arm/Abdomen
    - N=26 minimum
  - Abdomen/Abdomen/Arm

- N=26 minimum
- FST Schedule
  - Duration of FST and Challenges - **Random Assignment**
    - 4 x 8 hours FST
    - Hypoglycemic or Hyperglycemic challenges will be randomly assigned to each FST. These assignments are recommendations and investigator discretion may be used in selecting which challenge is to be performed for each FST.
      - Two Hyperglycemic Challenges
      - Two Hypoglycemic Challenges
      - Regardless of the order these challenges are performed, a total of 2 hyperglycemic challenges and 2 hypoglycemic challenges should be targeted.
    - A minimum of N=20 subjects will undergo observation

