### 9.1. Study Design

The study is a multi-center, randomly assigned, prospective, single-sample correlational design without controls. Subjects will be randomly assigned to sensor location, FST day, and FST time.

It is expected that subjects 7 - 13 years will complete 2 days of YSI™\* FST with the Guardian™ Sensor (3) and subjects 2 - 6 years will complete 2 days of SMBG FST with the Guardian™ Sensor (3). Subjects ages 2 – 6 years will only do SMBG during their FST.

Subjects will wear Guardian™ Sensor (3)s in the following configurations outlined in Table 6 and Table 7:

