## Hypoglycemic and Hyperglycemic Challenges

### **Subjects 2 - 13 years:**

During the day of YSI™\*/SMBG FST, subjects (2 - 13 years) will not participate in hypoglycemic and hyperglycemic challenges.

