## 15.7. Assignment to Day of YSI™\* FST

Adult subjects and subjects with age of 14 - 80 will be required to attend four 8-hour sessions of frequent sampling in which agreement between YSI™\* and Guardian™ Sensor (3)s connected to the Guardian™ Connect Transmitters will be evaluated.

Pediatric subjects with age of 7 – 13 will be required to attend two 6-hour sessions of frequent sampling in which agreement between YSI™\* and Guardian™ Sensor (3)s connected to the Guardian™ Connect Transmitters will be evaluated.

Pediatric subjects with age of 2 – 6 will be required to attend two 4-hour sessions of frequent sampling in which agreement between SMBG and Guardian™ Sensor (3)s connected to the Guardian™ Connect Transmitters will be evaluated.

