Testing on human subjects is necessary to characterize the accuracy of this sensor algorithm. For purposes of this study, subjects will wear the study devices with Guardian™ Sensor (3). Subjects will manage their diabetes independent of the Guardian™ Sensor (3) values. During YSI™*/SMBG FST, venous blood glucose concentrations or SMBG (subjects 2-6 years only) will be measured periodically; these values will be compared to sensor glucose values (SGVs) in order to determine sensor accuracy.

Accuracy data will be calculated based on comparing calibrated glucose sensor values to a "gold standard" (Yellow Springs Instrument [YSI™*] plasma glucose values) in subjects during YSI™* frequent sample testing (FST). The YSI™* glucose analyzer, Model 2300, has been the recognized standard for the measurement of blood glucose and will be utilized across the investigational centers for the tests.

4. Study Objectives

The primary objective of the study is to demonstrate the accuracy of Guardian™ Sensor (3) when used over a period of 7 days (i.e., 170 hours) with the system in subjects 2-80 years of age.

5. Investigation Plan

The study is a multi-center, randomly assigned, prospective, single-sample correlational design without controls. Subjects will be randomly assigned to sensor location, FST day, and FST time.

A total of up to 460 previously-diagnosed type 1 and 2 diabetes subjects will be enrolled in order to have 244 subjects (122 adults and 122 pediatrics) complete study.

- Cohort1 (Adults): N= 122 subjects 18-80 years old
 - N= 15 minimum subjects age 18-29 years old
 - N= 15 minimum subjects age 30-60 years old
 - N= 15 minimum subjects age 61-80 years old
- Cohort2 (Pediatrics): N= 122 subjects 2-17 years old
 - N= 15 minimum subjects 2-4 years old
 - N= 15 minimum subjects 5-6 years old
 - N= 20 minimum subjects 7-10 years old
 - N= 20 minimum subjects 11-13 years old
 - N= 24 minimum subjects 14-17 years old

6. Determination of Sample Size

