7.3 Center Pooling

Data will be pooled per cohort for analysis.

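### Pooled pediatric by-day ARE and bias mix ages 7-13 and 14-17 in proportions that change with the wear day, so a Day 4 to 5 change could reflect who was tested rather than sensor wear

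*SAP*

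**What the plan says.** SAP 7.9.9 and Protocol 15.11.6 plan summary statistics for ARE and for bias against YSI. ARE relative to the YSI "reference will be calculated for each day separately", and bias is likewise given for each day. Neither section names an age or challenge stratum for these by-day figures.

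Protocol 15.8.1 divides the datasets by age only at 18, giving 18-80 and 2-17. SAP section 5 defines "Cohort2 (Pediatrics): N= 122 subjects 2-17 years old", and SAP 7.3 adds: "Data will be pooled per cohort for analysis".

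Inside that pediatric cohort the testing differs by age:

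- Ages 14-17 follow the 14-80 schedule, which Protocol 15.7 describes as "four 8-hour sessions of frequent sampling". For these subjects "a total of 2 hyperglycemic challenges and 2 hypoglycemic challenges should be targeted" (Protocol 7.6).
- Ages 7-13 have "two 6-hour sessions of frequent sampling" (Protocol 15.7). Protocol 9.1 says that ages 2-13 "will not participate in hypoglycemic and hyperglycemic challenges".
- Ages 2-6 have no YSI reference: "Subjects ages 2 – 6 years will only do SMBG during their FST" (Protocol 9.1). They add nothing to the YSI-based ARE and bias.

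**The concern.** The primary objective is accuracy over a 7-day wear, so by-day ARE and bias are the natural place for a reader to look for a change in accuracy as the sensor ages. That reading needs the same kind of subject, tested in the same way, on each day. The two YSI-tested pediatric bands are concentrated on different days: 14-17 on Day 4 and 7-13 on Day 5. They also differ in session length and in whether glucose challenges are used. If accuracy differs between the bands, a pooled pediatric table carries part of that difference into the day-to-day pattern, and the planned tables give no means of separating it from a wear effect.

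**Working it through.** The plan gives no figure of its own here, so the check starts from the FST timing tables (Protocol 7.6, repeated in 8.1 and 9.1).

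**Groups tested on each wear day**

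- Ages 14-17 (14-80 table, six groups): A1, A2 and B1 test on Days 1, 3, 4 and 7; B2, C1 and C2 test on Days 2, 4, 5 and 6. Day 4 has 6 of 6 groups; every other day has 3 of 6.
- Ages 7-13 (eight groups): the A groups test on Days 1 and 7, B on 2 and 5, C on 3 and 5, D on 4 and 6. Day 5 has 4 of 8 groups; every other day has 2 of 8.

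**Share of YSI session time from ages 14-17**

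Inputs: minimum 24 subjects aged 14-17, and minimum 20 + 20 = 40 aged 7-13 (SAP section 5); 8-hour and 6-hour sessions (Protocol 15.7). Equal allocation across FST groups is assumed, because the documents state no ratio.

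Share on day d = (n14-17 × fraction tested × 8) / (n14-17 × fraction tested × 8 + n7-13 × fraction tested × 6)

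| Day | 14-17 hours | 7-13 hours | 14-17 share |
|---|---|---|---|
| 4 | 24 × 1.0 × 8 = 192 | 40 × 0.25 × 6 = 60 | 192/252 = 76.2% |
| 5 | 24 × 0.5 × 8 = 96 | 40 × 0.50 × 6 = 120 | 96/216 = 44.4% |
| Others | 24 × 0.5 × 8 = 96 | 40 × 0.25 × 6 = 60 | 96/156 = 61.5% |

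The Day 4 to 5 drop in share is 31.7 percentage points. One sample per 15 minutes in both bands gives the same shares for YSI pairs (32 per 8 hours, 24 per 6 hours).

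**Sensitivity of the shares**

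The age-band minimums sum to 15 + 15 + 20 + 20 + 24 = 94, which leaves 122 − 94 = 28 completers unassigned.

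| Scenario | Day 4 | Day 5 | Drop (points) |
|---|---|---|---|
| All 28 aged 14-17 (52 and 40) | 87.4% | 63.4% | 24.0 |
| All 28 aged 7-13 (24 and 68) | 65.3% | 32.0% | 33.3 |
| Minimums, strict 24-hour days (72-96 h, 96-120 h) | 75.4% | 48.6% | 26.8 |
| Minimums, unequal allocation (40-60% in the Days 1, 3, 4, 7 groups at 14-17; 40-60% in the B and C groups at 7-13) | 73-80% | 35-55% | 18 to 45 |

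The share falls from Day 4 to Day 5 in every case.

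**Effect on a pooled by-day mean**

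Let mT and mC be the mean ARE (or bias) at ages 14-17 and 7-13, constant over wear, and s the 14-17 share. Then

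pooled mean on day d = s(d) × mT + (1 − s(d)) × mC

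Day 4 minus Day 5 = (0.762 − 0.444) × (mT − mC) ≈ 0.32 × (mT − mC)

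The documents give no accuracy by age band or challenge, so mT − mC is an assumption. If it is 0, the artifact is 0. At ±1 ARE point it is ±0.3 points, at ±3 it is ±1.0, and at ±5 it is ±1.6.

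**The case against.** The strongest reply is that a shift in mix moves a mean only if the two bands differ, and nothing in the documents shows that they do. This stands. A reader might infer from the schedule that the pediatric tables will show a false fall in ARE from Day 4 to Day 5. The documents do not support that. Even the direction is open. Ages 7-13 have provocations of their own: exercise of at least 60 minutes at the start of the session when glucose is within a stated range, and at least an hour lying on the sensors (Protocol 9.2.2.6.2). Ages 14-80 also have the compression procedure, but exercise there belongs to a selected cohort.

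Other parts of the reply also stand:

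- Challenge assignments are recommendations, and some subjects aged 14-80 are observed only. The challenged share is therefore at most the 14-17 share.
- The two-fold concentration on Day 4 and Day 5 rests on equal allocation. Only the testing of every 14-17 group on Day 4 is independent of it.
- SAP 7.9.9 does not define day, and it mentions 3 study days for the Bland-Altman plots. Timing windows of up to ±6 hours can carry sessions across a day boundary.
- Sampling every 5 minutes below 75 mg/dL (Protocol 10.5.1) can make shares of pairs differ from shares of hours.
- SAP 7.3 is headed as center pooling. The single 2-17 dataset in Protocol 15.8.1 is the firmer support for pooling across age.
- No planned hypothesis test, alpha or stopping decision uses by-day ARE or bias.

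The reply that the subgroup analyses already cover the matter does not stand. Those in SAP 7.9.9 concern the 20% agreement rate and those in 7.9.10 the home-use data. None is by day. They may show whether accuracy differs with age, but they do not take the age mix out of the daily figures.

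**Conclusion.** The point holds as a possible confound in descriptive output. As planned, a Day 4 to 5 change in pooled pediatric ARE or bias cannot be separated from a change in age band and test procedures. The shift in mix is large, from about 76% to 44% aged 14-17 under the base assumptions, and keeps its direction in every scenario tried. The resulting artifact is about one third of whatever difference exists between the bands, of either sign, and zero if there is none.

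This rests on equal allocation, on wear days as labelled in the FST tables, on the planned minimums, and on pooled by-day figures for the whole 2-17 dataset. The adult cohort follows one schedule, so this mixing of two schedules does not arise there.

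**What to change.** In SAP 7.9.9 and Protocol 15.11.6, report pediatric by-day ARE and bias separately for ages 7-13 and 14-17, with the number of subjects and pairs in each cell. Where a pooled pediatric by-day figure is also shown, standardise every day to the same age-band weights, for example each band's overall share of YSI readings. At the minimums and by session time, the 14-17 weight would be (24 × 32)/(24 × 32 + 40 × 12) = 768/1248 = 61.5% on every day, so the change in mix becomes zero. State in the same place that day means sensor wear day, and how a session that crosses a boundary is assigned.

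The cost is SAP and protocol wording and one stratified table from data already collected. The downside is small cells: on an ordinary day at the minimums, about 12 subjects aged 14-17 and 10 aged 7-13. Single-day figures by band will be noisy, which is why counts should accompany them and why the standardised pooled figure is worth keeping. Standardising by age band does not remove any difference between days in the challenges actually performed within ages 14-17.

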## 7. Selection of Subjects

### 7.1. Study Population

A total of up to 460 previously-diagnosed type 1 and 2 diabetes subjects will be enrolled in order to have 244 subjects complete study.

- N= 122 subjects 18-80 years old
  - N= 15 minimum subjects age 18-29 years old
  - N= 15 minimum subjects age 30-60 years old
  - N= 15 minimum subjects age 61-80 years old
- N= 122 subjects 2-17 years old
  - N= 15 minimum subjects 2-4 years old
  - N= 15 minimum subjects 5-6 years old
  - N= 20 minimum subjects 7-10 years old
  - N= 20 minimum subjects 11-13 years old
  - N= 24 minimum subjects 14-17 years old

Up to 17 investigational centers in the US will be used during the study.

Subjects will be grouped by age, diabetes classification, body mass index (BMI)/ weight, CGM experience, glycosylated hemoglobin (HbA1c), exercise activity, and compression procedure.

- **Diabetes cohorts based on insulin requirement**

- 18-80 years
  - Insulin requiring N = minimum 78 subjects
    - N= minimum of 52 type 1 insulin requiring
    - N= minimum of 26 type 2 insulin requiring
  - Non-Insulin requiring N = minimum 12 subjects
- 14 - 17 years
  - Insulin requiring N = minimum 24 subjects
- 2 - 13 years
  - Insulin requiring N = minimum 10 subjects

- **Diabetes cohorts based on Centers for Disease Control and Prevention (CDC) classification for 20 years old or younger**

A description of the following 4 groups will be performed:

- Underweight subjects (less than (<) 5th percentile): N=minimum of 1 subjects
- Normal weight subjects (5th percentile to less than (<) 85th percentile): N= minimum of 40 subjects
- Overweight (85th to less than (<) the 95th percentile): N= minimum of 8
- Obese subjects (greater than or equal to (≥) the 95th percentile): N=minimum of 1 subjects

- **Diabetes cohorts based on BMI according to WHO criteria [World Health Organization, 2011] for subjects greater than 20 years old:**

A description of the following 5 groups will be performed:

- Underweight subjects (BMI less than (<)18.5 kg/m^2): N=minimum of 1 subject
- Normal weight subjects (BMI 18.5 to 24.99 kg/m^2): N= minimum of 28 subjects
- Overweight and obese subjects (BMI 25.00 to 40 kg/m^2): N= minimum of 36 subjects
  - Overweight subjects (BMI 25.00 to 29.99 kg/m^2)
  - Obese subjects (BMI 30.00 to 39.99 kg/m^2)
- Morbidly obese subjects (BMI greater than or equal to (≥)40 kg/m^2): N=minimum of 1 subject

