**Figure 3. Visit Schedule Subjects 14-80 years**

### 8.2.2.2. Visit 1: Consent and Screening

#### Overview General

##### Investigational center staff will:

- Obtain California Experimental Subject's Bill of Rights (if applicable), Informed Consent Form (ICF) /Assent form, and HIPAA form from the subjects
- Assess subject eligibility to participate in the study
- Obtain demographic and baseline characteristics including:
  - Age
  - Gender
  - Race
  - Ethnicity
  - Prior medical history
  - Height and Weight

Note: BMI will be calculated automatically in the study database, based on height and weight measurements entered.

  - Concomitant medications (Screening Only)
  - Date of diabetes diagnosis
  - Insulin carbohydrate ratio and insulin sensitivity for subject's insulin requiring, if applicable
- Complete required screening tests, if all eligibility criteria are met:
  - Perform urine test for pregnancy, female subjects of child bearing age or capability
  - Obtain blood sample:
    - Hct
      - Send to Central Laboratory, or clinic's own lab for required screening tests. There is no point of care (POC) testing for Hct.
      - If patient has prior Hct from routine care done within 6 months of enrollment and the report of lab placed with subject source documents, then no blood needs to be done.
    - HbA1c (not an eligibility criteria)
      - Send to Central Laboratory
- **Note:** For all out of range lab results, a single re-test is permitted
- Per Investigator's discretion, subjects may participate in the exercise cohort. Exercise cohort subjects will be asked to exercise for a minimum of 30 minutes a day during the hyperglycemic challenge YSI™\* FSTs.

- Enter electronic Case Report Forms (eCRF)s into the study database as appropriate
- Schedule next visit date and time

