# CIP324 Clinical Investigation Plan

10838519DOC

Version H

Page 80 of 173

Medtronic

- Only subjects who have been previously established for participation in Exercise Cohort during Visit 1 can participate in the Exercise Cohort activities during YSI™\* FST.
- A subject who qualified at Visit 1 for participation in Exercise cohort is expected to exercise during hyperglycemic challenge at YSI™\* FST days.
- Exercise will take place at the Investigator's discretion during the YSI™\* FST visit. Subjects may exercise during the observation period based on Investigator's discretion.
- See Hyperglycemic Challenge Guidelines for exercise guidelines. Exercises will not occur during the Hypoglycemic challenges.
- Procedures:
  - Exercise will consist of treadmill or stationary bicycle. Others forms of exercise may be allowed with sponsor permission.
  - Subjects who normally exercise more than 30 minutes at home will be allowed to exercise longer than 30 minutes during the study as long as the subject does not become hypoglycemic.
  - Exercise will be terminated if subjects develop chest pain.
  - Exercise is not being performed to induce hypoglycemia but rather to collect data on the Guardian™ Sensor (3) performance under stress conditions.

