## **Compression procedure:**

Subjects will be asked to lay on their sensors for at least one hour for each YSI™\* FST. Time, duration, and activity will be collected based on sensor location on an eCRF for subjects 18-80 years old (See Table 4) and subjects 14-17 years old (See Table 5):

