### **Exercise:**

Subjects are required to begin exercise at start of YSI™\*/SMBG FST if their glucose is between 100-300 mg/dL mg/dL. They should continue exercise for at least 60 minutes. This exercise can be in the form of playing or moving around. We recommend the sites provide toys and games for young subjects to use during the exercise period. However, exercise should be stopped, and meal administered and/or glucose given when:

- Glucose is less than or equal to 70 mg/dL for subjects 2-6 years of age
- Glucose is less than or equal to 65 mg/dL for subjects 7-13 years of age

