- **Diabetes cohorts based on BMI according to WHO criteria [World Health Organization, 2011] for subjects greater than 20 years old:**

A description of the following 5 groups will be performed:

- Underweight subjects (BMI less than (<)18.5 kg/m^2): N=minimum of 1 subject
- Normal weight subjects (BMI 18.5 to 24.99 kg/m^2): N= minimum of 28 subjects
- Overweight and obese subjects (BMI 25.00 to 40 kg/m^2): N= minimum of 36 subjects
  - Overweight subjects (BMI 25.00 to 29.99 kg/m^2)
  - Obese subjects (BMI 30.00 to 39.99 kg/m^2)
- Morbidly obese subjects (BMI greater than or equal to (≥)40 kg/m^2): N=minimum of 1 subject

- **Diabetes cohorts based on prior real-time CGM experience (by self report)**

- CGM naïve: N= minimum of 40 subjects (2-80 years)
- CGM experienced: N= minimum of 40 subjects (2-80 years)

- **Diabetes cohorts based on HbA1c:**

- Baseline HbA1c (by certified National Glycohemoglobin Standardization Program, NGSP, method) will be collected:
  - A description of the following 3 groups will be performed: HbA1c less than (<) 7%, HbA1c 7-9%, HbA1c greater than (>) 9%
- Quartile comparison (lowest to the highest) based on HbA1c

- **Diabetes cohort based on exercise activity:**

- 18 – 80 years
  - N=minimum of 22 subjects
- 14 - 17 years
  - N= minimum of 6 subjects
- 2 - 13 years
  - N= minimum of 20 subjects
- Sponsor may instruct site for exercise to be performed in order to obtain low glucose values

- **Diabetes cohort based on compression procedure:**

- 18 – 80 years

- N=minimum of 22 subjects
- 14 - 17 years
  - N= minimum of 6 subjects
- 2 - 13 years
  - N= minimum of 10 subjects

All analysis follow the definitions provided in: Performance Metrics for Continuous Interstitial Glucose Monitoring: Approved Guideline, CLSI POCT05-A [Klonoff et al. 2008].

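### Exercise and compression accuracy is described by whole-subject cohort, so the stressed readings are diluted, most heavily for exercise at ages 14-80

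*SAP*

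**What the plan says.** Protocol 7.1 sets the unit of grouping: "Subjects will be grouped by age, diabetes classification, body mass index (BMI)/ weight, CGM experience, glycosylated hemoglobin (HbA1c), exercise activity, and compression procedure". The exercise minimums are 22 subjects (18-80 years), 6 (14-17) and 20 (2-13). The compression minimums are 22, 6 and 10.

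The planned output in SAP 7.9.9 and Protocol 15.11.6 is a "Descriptive subgroup analysis of Guardian™ Sensor (3) performance", using the 20% agreement rate with a 20 mg/dL rule when the reference is below 70 mg/dL. It is reported for each cohort, including the "Diabetes cohort based on exercise activity" and the "Diabetes cohort based on compression procedure". Neither document restricts the rate to pairs taken during or after the stress, or sets stressed against unstressed time within a subject. The home-use analysis (SAP 7.9.10) also lists exercise activity among its subgroups.

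The procedures are as follows.

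- Exercise, ages 14-80 (Protocol 8.2.2.2): "Exercise cohort subjects will be asked to exercise for a minimum of 30 minutes a day during the hyperglycemic challenge" sessions. Protocol 8.2.2.6.3 excludes exercise from hypoglycemic challenges, allows it during observation, and gives its purpose as data on sensor "performance under stress conditions".
- Exercise, ages 2-13 (Protocol 9.2.2.6.2): begins at the start of the FST if glucose is 100-300 mg/dL. "They should continue exercise for at least 60 minutes".
- Compression, all ages (Protocol 8.2.2.6.3 and 9.2.2.6.2): "Subjects will be asked to lay on their sensors for at least one hour for each" FST. Time, duration and activity go on an eCRF by sensor location. Tables 4, 5 and 8 direct the compression at the location that holds two sensors.

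**The concern.** A cohort rate built from all of a subject's FST readings answers whether people who exercised had accurate sensors over the whole of testing. It does not answer whether the sensor was accurate while they exercised. When the stressed interval is short, the first quantity says almost nothing about the second. A real loss of accuracy during exercise or compression would be averaged with a much larger number of unstressed readings, and the table would look reassuring for that reason alone.

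What is at stake is one descriptive result whose purpose, for exercise, the protocol states. The raw data for a better answer are largely being collected already.

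**Working it through.** The documents give no expected rate, precision or power for these cohorts, so there is no planned figure to reproduce.

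**Inputs**

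- FST time (Protocol 7.6): ages 14-80, 4 x 8 h = 1,920 min; ages 7-13, 2 x 6 h = 720 min; ages 2-6, 2 x 4 h = 480 min (fingerstick reference only).
- Exercise, ages 14-80: at least 30 min in each hyperglycemic session (Protocol 8.2.2.2), two such sessions targeted (Protocol 7.6), so 60 min. If done at all four sessions under observation, 120 min.
- Exercise, ages 2-13: at least 60 min x 2 sessions = 120 min.
- Compression: at least 60 min per FST, so 240 min at ages 14-80 and 120 min at ages 2-13.
- Primary sensors (Protocol 15.8.1): from age 7, one primary sensor in each of two locations. Only the doubled location is compressed, so the compression share across both primary sensors is halved.
- Sampling (Protocol 10.5.1, ages 7-80): every 15 min at 75 mg/dL or above, every 5 min below.

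**Formulas.** Share f = stressed minutes / FST minutes. Shift in the cohort rate = f x d, where d is the loss of agreement during stress. The values of d are illustrations, not document figures.

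| Age and stress | f | Shift, d = 10 | d = 20 | d = 30 |
|---|---|---|---|---|
| 14-80 exercise, two sessions | 60/1,920 = 3.1% | 0.3 | 0.6 | 0.9 |
| 14-80 exercise, four observed sessions | 120/1,920 = 6.25% | 0.6 | 1.25 | 1.9 |
| 14-80 compression, compressed location | 240/1,920 = 12.5% | 1.25 | 2.5 | 3.75 |
| 14-80 compression, both primary sensors | 12.5%/2 = 6.25% | 0.6 | 1.25 | 1.9 |
| 7-13 exercise; compression, compressed location | 120/720 = 16.7% | 1.7 | 3.3 | 5.0 |
| 7-13 compression, both primary sensors | 16.7%/2 = 8.3% | 0.8 | 1.7 | 2.5 |
| 2-6 exercise; compression, compressed location | 120/480 = 25% | 2.5 | 5.0 | 7.5 |

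**Extreme case.** Assume 85% agreement when unstressed and none at all during exercise. The 14-80 exercise cohort would still report 0.85 x (1 - 0.03125) = 82.3%, or 0.85 x (1 - 0.0625) = 79.7% with exercise at all four sessions.

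**By pairs rather than time, ages 14-80.** At 15-minute sampling a sensor yields 32 x 4 = 128 pairs, of which 1 x 4 = 4 fall in exercise (3.1%). If each of two hypoglycemic sessions spent 2 h below 75 mg/dL (assumption), the total is 2 x 2 x 12 + 28 x 4 = 160 pairs and the share falls to 4/160 = 2.5%.

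**Size of the stressed cells.** For 22 adults, 22 x 4 = 88 exercise pairs per location out of 22 x 128 = 2,816. For six adolescents, 6 x 4 = 24. Compression gives 4 x 4 = 16 pairs per compressed sensor.

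**Mixing of the two stresses.** A challenge subject aged 14-80 who does both has about 1 h of exercise and 4 h of compression, so the exercise-cohort rate contains more compression than exercise.

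**The case against.** The best counter-argument is that neither document says which pairs enter the exercise and compression rows, so a restriction to stress intervals is not excluded, and the compression log would support one. This does not carry. Protocol 7.1 groups subjects, the minimums count subjects, and these rows stand in the same list as BMI and HbA1c with no further rule. The plain reading is a rate over all of the subject's pairs.

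Several other points stand.

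- The only stated objective is accuracy over 7 days, and the subgroup analysis is descriptive. A reader might infer that the trial will declare exercise or compression to have no effect. No test or stressed-versus-unstressed contrast is planned, so the documents do not support that.
- The stress purpose is stated for exercise only; none is given for compression. The cohort entry itself also says the sponsor may instruct exercise to obtain low glucose values.
- Dilution is not severe everywhere. At ages 2-6 an assumed 30-point loss would shift the rate by 7.5 points, which would be visible. All durations are minimums, so actual shares may be larger.
- A reader might infer that no unstressed comparison group exists, because compression is worded for all subjects and exercise is required at ages 2-13. The text is not that clear. Protocol 9.2.2.2 makes the exercise cohort discretionary at ages 2-13, Protocol 9.2.2.6.2 applies only within a glucose range, and from age 7 sensors outside the doubled location are not targeted for compression.
- A reader might infer that exercise times are not recorded. The eCRFs and the challenge guidelines are under separate cover, so this cannot be judged here.
- Comparing exercise pairs with all other FST pairs would be a poor remedy. Challenge subjects do not exercise in hypoglycemic sessions, and the agreement rule changes below 70 mg/dL, so exercise would be confounded with glucose range.

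**Conclusion.** The point holds as a worthwhile improvement to a descriptive analysis. At ages 14-80 the planned exercise-cohort rate is nearly insensitive to what happens during exercise (3.1% of FST time, 6.25% at most under the four-session observation scenario at minimum duration). The compression-cohort rate heavily dilutes any loss (12.5% in the compressed location, about 6.3% across both primary sensors). The dilution is milder at ages 7-13 (16.7%; about 8.3% for compression across both primary sensors) and at ages 2-6 (25%). The shares rest on the stated minimum durations and the targeted two hyperglycemic sessions; the sizes of loss are assumptions. No primary or secondary endpoint changes.

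**What to change.** In SAP 7.9.9 and Protocol 15.11.6, add a descriptive reading-level analysis:

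1. Flag each pair as inside or outside the logged exercise or compression interval, with any recovery window fixed before data review.
2. Compare exercise pairs with non-exercise pairs from the same sessions, or the same session type, of the same subjects, by sensor location. This keeps hypoglycemic-challenge readings out of the contrast.
3. For compression, count only sensors in the compressed location.
4. Report pairs with overlapping exercise and compression separately.
5. Confirm that exercise start and stop times are captured on the eCRF or FST log, and add them if not.
6. Keep the cohort minimums as recruitment targets.

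Two sets of passages also need reconciling: Protocol 9.2.2.2 with 9.2.2.6.2 on whether exercise at ages 2-13 is discretionary or required, and the compression minimums in Protocol 7.1 with 8.2.2.6.3 and 9.2.2.6.2 on whether compression applies to every subject.

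The cost is SAP and protocol wording, a flag in the pair dataset and possibly two time fields. No visit is added. The downside is few stressed pairs, about 4 exercise pairs per sensor at ages 14-80, and clustered within subject, so the estimates will be wide and should be shown with their pair and subject counts.
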